8.2 Study procedures, assessments, and participant activities

8.2.1 Screening procedures

Potential participants will be screened for their duration into survivorship (needs to be 4 months–5 years), age (needs to be ≥ 18 years old), and BMI (needs to be >20 kg/m²). Potential participants also need to be in the habit of consuming food within a window that is larger than 10 hours and be experiencing fatigue (a score of 3 or higher on a scale of 0-10 for their worst fatigue in the last week). If there are any screen failures, we will retain the information in a screening log as described in §6.2 to avoid approaching them again.

8.2.2 Source of record or measures

The Clinical Record contains height, weight, current menopausal status, Karnofsky Performance Status or Eastern Cooperative Oncology Group (ECOG) Performance Status, comorbidities, cancer stage, surgical procedures, types and doses of treatments, and other clinical characteristics. The study team will use the medical record to complete as much of the Clinical Record as possible. The study team will also note all toxicity outcomes. All other questionnaires will be completed by the participant.

8.2.3 Research data in the medical record

Documentation of study participation will be included in the medical record by means of uploading a signed consent form to each participant's medical record, for those participants enrolled in the research study. No further research-related information will be included in the medical record.

The assessments will take place in one of two locations: 1) at the Wilmot Cancer Institute (including satellite locations) and 2) at home or participant's choice. The consent will take place at the clinic whenever possible, which comprises the Wilmot Cancer Institute, Pluta Cancer Center, or a Wilmot Cancer Institute-affiliated clinic, or can alternatively be accomplished remotely. The questionnaires will be completed electronically or on paper and can be completed at the clinic or at home (or wherever is convenient). Body weight data will be collected by the participant at their home using a portable bathroom scale that is provided by the study team. Therefore, this entire study can be completed remotely.

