Also, to ensure safety in regard to caloric intake, participants will complete a 24-h Food Record before the intervention (their normal diet and dietary pattern). This will be done prospectively on any day before they begin the TRE intervention. The 24-h Food Record entails noting the identity of the food, the quantity, and the time it was ingested. They will also complete a prospective 24-h Food Record, including times, on Day 14, the last day of the intervention. The Food Record will be analyzed for total calories, macronutrients, micronutrients, and bioactive compounds using Nutrition Data System for Research (NDSR; Regents of the University of Minnesota, Minneapolis, MN) or a similar program.

An exploratory aim of this study is cancer-related fatigue, as assessed using the FACIT-F, BFI, and Symptom Inventory. Patients will complete these instruments at baseline and post-intervention.

1. Functional Assessment of Chronic Illness-Fatigue (FACIT-F) questionnaire: The FACIT-F is a 40-item, validated, commonly used measure of fatigue that is comprised of five subscales: physical well-being, social well-being, emotional well-being, functional well-being, and fatigue.²² It captures symptoms in these categories over the last 7 days.
2. Brief Fatigue Inventory (BFI): The BFI is a 10-item fatigue questionnaire that is also validated and commonly used.²³ It captures fatigue *now* and the usual and worst in the last 24 h. It also includes 6 single-item questions regarding how fatigue has interfered with general activity, mood, work, etc.
3. Symptom Inventory (SI): The symptom inventory (modified from the MD Anderson Symptom Inventory²⁴) includes 19 items that are common in the cancer experience (e.g., pain, distress, lack of appetite, numbness and tingling, fatigue), as well as 8 items related to how much these symptoms interfere with activities of daily living and quality of life. As many symptoms often correlate with each other including fatigue (i.e., symptom clustering²⁵), it is important to capture the change in many symptoms from baseline to post-intervention. Exploratory analyses will probe whether adherence to the diet or high consumption of any dietary component correlates with the change in any of these symptoms over the two-week intervention.

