8.2.5 Schedule of assessments

After consenting to the study, the participant can decide to start the intervention any day within the next week. Preferably, the 24-h Food Record and baseline questionnaires will be performed the day before the intervention begins (Day 0) and body weight will be measured on the first day of the intervention (Day 1), but participants will be given up to 3 days to begin in case there are technical difficulties with REDCap or other barriers to starting the intervention. Similarly, it is preferred that post-intervention questionnaires are completed the day after the intervention ends (Day 15), but up to 3 days will be allowed. On Day 8, the participant will provide body weight. The Day 14 24-h Food Record should be performed on Day 14, but can be completed on Day 12, 13, or 14 if there are anticipated logistical reasons why completion of the diary on Day 14 would not be possible. Post-intervention exit interviews will be performed with a member of the study team within one week of completing the intervention. Participants will be asked to complete the daily diaries every day at the end of the day.

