8.2.7 Data collection tables

A Clinical Record form will be completed by the study team using the medical record. These following table lists study-related activities that the participants will experience.

Assessment or Activity	Study Goal	Assessment Location	Baseline (approx. Day 0)	Intervention Day 1	Intervention (Day 1-14)	Intervention Day 8 (approx.)	Intervention Day 14 (approx.)	Post-intervention (approx. Day 15)
On-study data form	Demographics and clinical characteristics	Clinic or home (REDCap*)	✓					
24-h Food Record	Safety	Home	✓				✓	
Functional Assessment of Chronic Illness-Fatigue (FACIT-F)	Exploratory	Clinic or home (REDCap*)	✓					✓
Brief Fatigue Inventory (BFI)	Exploratory	Clinic or home (REDCap*)	✓					✓
Symptom inventory	Exploratory	Clinic or home (REDCap*)	✓					✓
Body weight	Safety	Clinic or home		✓		✓		✓
Daily diary	Primary aim	Home (REDCap*)			Every day, at the end of the day			
Check-in	Check-in	Remote				✓		
Exit interview	Exploratory	Clinic or home (telephone)						✓

*If a participant prefers, they may complete paper-based versions of these assessments and return them to the study team in-person or in a postage-paid envelope.

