9.1.2 Hunger and hunger-related symptoms due to the intervention

For most participants, eating within only a 10-h window will mean re-adjusting their typical eating pattern. Many participants will need to rearrange their meal times—either delay breakfast or eat dinner earlier. If they delay breakfast, they might feel hungry in the few hours leading up to their eating window, especially in the first few days of the study. Similarly, they might crave something before bed if they are in the habit of eating before bed. With hunger can come lack of concentration, fatigue, dizziness, irritability, and other symptoms. All participants will be encouraged to stay hydrated and to consume a snack outside of the window if symptoms become debilitating.

Probability: Moderate

Magnitude: Low to moderate

Duration: Short-term

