17.2 Statistical analysis

The primary objective of this study is to assess the feasibility of delivering a TRE intervention to cancer survivors by way of adherence. As the primary endpoint, we will determine how many days the participants were able to restrict their eating to the 10-h window. Success will be deemed if participants on average reach the fasting target at least 11 of the 14 days (79% of days). This goal is based on prior TRE studies.^{17,21} A secondary aim is retention; it is hypothesized that at least 80% (32 out of 40) of those who provide baseline data also provide post-intervention data; this goal is based on prior studies conducted by the Division of Cancer Control.

To ensure safety of this intervention, body weight will be monitored weekly from baseline to post-intervention. It is anticipated that no one will lose more than 3% body weight in one week or 5% body weight over the 14 days.

In exploratory analyses, we will assess fatigue and well-being from the FACIT-F and BFI questionnaires, as well as general symptoms from the Symptom Inventory. The distribution of the outcome measures at baseline, at 14 days, and the change score (from baseline to 14 days) will be first assessed visually (e.g., histogram) and then descriptive statistics [e.g., range, interquartile range, mean (95% confidence interval), standard deviation] will be evaluated. The magnitude of the change score together with variability and distribution data will be used to inform the sample size and design of our future study. A paired t-test will be used to formally assess whether the change over time was different from zero with a two-tailed α of 0.10. For a particular outcome measure, $n=32$ patients provides 80% power to detect changes at the magnitude of 0.45 of the measured variability estimated by the standard deviation.

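### Baseline and post-intervention fatigue questionnaires are not matched on place or time of day, so a change of setting can enter the exploratory paired change, mainly for the BFI

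*Combined protocol and SAP*

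**What the plan says.** Section 8.2.3 leaves the setting open: "The questionnaires will be completed electronically or on paper and can be completed at the clinic or at home (or wherever is convenient". The table in 8.2.7 repeats this for the FACIT-F, BFI and Symptom Inventory, whose location is given as "Clinic or home (REDCap" for both time points. Section 8.2.5 gives preferred days, with up to 3 days' leeway, but no hour. Of the first set it says "Preferably, the 24-h Food Record and baseline questionnaires will be performed the day before the intervention begins (Day 0", and of the second "it is preferred that post-intervention questionnaires are completed the day after the intervention ends (Day 15".

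Two other measures are tied to a time. Section 4.4 asks for weighing in the morning before intake, on the same hard surface where possible, and 8.2.5 puts the diary at the end of the day.

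Section 4.4 describes the BFI as asking about fatigue now and "the usual and worst in the last 24 h". It gives the FACIT-F a 7-day recall and states no recall period for the Symptom Inventory. For the analysis, 17.2 says: "A paired t-test will be used to formally assess whether the change over time was different from zero", at two-tailed alpha 0.10. It adds that the size and variability of the change will inform the future study.

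**The concern.** In a single-arm study, the pre-post change contains everything that differs systematically between the two assessments. If many participants fill in the first set around an oncology visit and the second at home, the change in surroundings and hour is added to any effect of the diet, and the plan has no means of separating them.

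The protocol itself gives a reason why the hour may matter. Section 9.1.2 says that participants who delay breakfast might find that "they might feel hungry in the few hours leading up to their eating window", and lists fatigue among the symptoms that hunger can bring. A rating of fatigue now could therefore depend on where in the eating window the form is completed.

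Two quantities are at stake, both exploratory: the mean change, which is tested against zero, and its SD, which feeds the next sample size calculation. A one-directional shift distorts the first; haphazard mismatch enlarges the second.

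**Working it through.** **Is a one-directional mismatch plausible?** Four provisions, read together:

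- 8.2.3: consent takes place at the clinic whenever possible.
- 6.1.1: consent may be taken on the day of an oncology appointment.
- 4.3: baseline questionnaires come after screening and consent.
- 8.2.4: the intervention should begin within 3 days of the baseline assessments.

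A participant who consents in clinic can complete the baseline forms there that day, do the food record at home, start within 3 days, and complete the second set at home. No clinic visit is required at the end. The plan permits this path but does not require it.

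**Reproducing the plan's figure.** Inputs from 17.2: n = 32, two-tailed alpha 0.10, effect 0.45 SD of the change. For a true standardised mean change δ, the paired statistic T follows a noncentral t with n − 1 = 31 degrees of freedom and noncentrality δ√n. The critical value is 1.696, and the rejection probability is P(T > 1.696) + P(T < −1.696). At δ = 0.45, the noncentrality is 0.45 × √32 = 2.546 and the power is 80.1%, which agrees with the stated 80%.

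**Systematic shift, no diet effect.** Assume a share q of participants changes setting in the same direction, and that this moves the score by d SDs of the change. The false mean change is then about q × d. Neither q nor d is in the documents. The table uses q = 0.5 and ignores the small extra variance from mixing switchers and non-switchers.

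| d (assumed) | Net shift q × d | Noncentrality | Chance of declaring a change |
|---|---|---|---|
| 0 | 0 | 0 | 10.0% |
| 0.04 | 0.02 | 0.113 | 10.2% |
| 0.10 | 0.05 | 0.283 | 11.3% |
| 0.20 | 0.10 | 0.566 | 15.2% |
| 0.30 | 0.15 | 0.849 | 21.4% |
| 0.40 | 0.20 | 1.131 | 29.8% |

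**Random mismatch.** If it raises the variance of the change by a fraction r, the SD grows by √(1 + r) and the standardised effect falls to 0.45/√(1 + r). The values of r are also assumed.

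| r (assumed) | SD multiplied by | Effect | Power at n = 32 | n for 80% power |
|---|---|---|---|---|
| 0 | 1.000 | 0.450 | 80.1% | 32 |
| 0.10 | 1.049 | 0.429 | 76.7% | 35 |
| 0.20 | 1.095 | 0.411 | 73.5% | 39 |
| 0.30 | 1.140 | 0.395 | 70.5% | 42 |

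**The case against.** The best case for the plan is that it permits a mismatch without building one in. Section 8.2.5 prefers the baseline forms on Day 0, alongside a food record that the 8.2.7 table places at home. The forms are available in REDCap, and the whole study can be done remotely. If most participants do both sets at home, the net shift may be close to nil: at 0.02 to 0.05 SD, the rejection rate is only 10.2% to 11.3%. The outcome is exploratory, and 8.1 does not expect large changes. Selection on baseline fatigue and participants' expectations already limit a causal reading, and the planned follow-on is a randomised trial. All of this stands, and it makes the point a modest one.

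A reader might also infer a weekday bias, since Day 0 and Day 15 are 15 days apart and 15 = 2 × 7 + 1. The documents do not support treating that as a defect. The start day is free, so a one-weekday offset should largely average out unless starts cluster. The FACIT-F's 7-day recall covers every weekday once. The weekend remark in 4.6 concerns social activities during the intervention, not the day on which forms are completed.

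Nor do the documents show the same sensitivity in all three instruments. The argument from the hour rests on the BFI, chiefly its rating of fatigue now; its usual and worst ratings span 24 hours.

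What remains is that place and hour are left free and are neither recorded nor used. How much setting contributed could therefore not be examined afterwards.

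**Conclusion.** The point holds as a cheap improvement to an exploratory analysis. Place and time of day may differ between a participant's two questionnaire sets, and the plan neither matches, records nor analyses them. A clinic baseline followed by a home follow-up is plausible under the plan's own workflow, and without a control arm its effect could not be told apart from that of the diet.

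The size is unknown. The 10% to 30% range rests on assumed net shifts of 0.02 to 0.20 SD. Its upper end requires, for example, half the participants to switch in the same direction with an effect of 0.4 SD. It would be wrong to read it as the study's expected false-positive rate, or to conclude that the fatigue change will be biased: if the mismatch is random, it adds noise only. The stated power of 80% is correct for its inputs, and the adherence endpoint is untouched.

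**What to change.** In 8.2.3, 8.2.5 and the 8.2.7 table, ask each participant to complete both sets of FACIT-F, BFI and Symptom Inventory in the same place, preferably at home, and at a similar time of day. Keep the Day 0 and Day 15 preference and the 3-day windows. Record place and completion time for each set in REDCap, including for paper forms. In 17.2, add a sensitivity analysis of the change limited to pairs matched on place and time of day, and state before analysis what counts as matched. That subset may be smaller than 32, so its results should be read descriptively.

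The cost is some protocol wording, two data fields and slightly less convenience for participants who would have done one set at a clinic visit.

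Moving baseline to the morning of Day 1 is not advised. For participants who delay breakfast, it could put the BFI rating of fatigue now at the point of pre-window hunger, and it would remove the leeway in 8.2.5. Weekday matching and a fixed limit in hours are not needed either.

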8.2.4 Duration of the study

Participants will participate in the study for approximately 3 weeks, including consent, baseline assessments, a 14-day intervention, post-intervention assessments, and an exit interview. After consent, each participant will need to complete a prospective, 24-h Food Record, after which the participant can begin the intervention. The participant can complete the Food Record, perform baseline assessments, and start the 14-day intervention any day within the first week of consent. However, the participant should begin the intervention within 3 days of completing baseline assessments and complete post-intervention assessments within 3 days of completing the intervention. The exit interview will be completed within 7 days of completing the intervention.

8.2.5 Schedule of assessments

After consenting to the study, the participant can decide to start the intervention any day within the next week. Preferably, the 24-h Food Record and baseline questionnaires will be performed the day before the intervention begins (Day 0) and body weight will be measured on the first day of the intervention (Day 1), but participants will be given up to 3 days to begin in case there are technical difficulties with REDCap or other barriers to starting the intervention. Similarly, it is preferred that post-intervention questionnaires are completed the day after the intervention ends (Day 15), but up to 3 days will be allowed. On Day 8, the participant will provide body weight. The Day 14 24-h Food Record should be performed on Day 14, but can be completed on Day 12, 13, or 14 if there are anticipated logistical reasons why completion of the diary on Day 14 would not be possible. Post-intervention exit interviews will be performed with a member of the study team within one week of completing the intervention. Participants will be asked to complete the daily diaries every day at the end of the day.

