4.1 Brief description and specific aims

This will be a single-arm feasibility pilot study among 40 cancer survivors with moderate to severe baseline fatigue. All participants in this study will be asked to follow a TRE meal pattern for 14 consecutive days. Participants will be encouraged to consume food and beverages only within a 10-h time window for the 14-day intervention, with the exception of water, which will be encouraged at any time. Participants will be allowed to take any of their normal medications at the prescribed times. Participants will be asked to complete a daily diary (every day for 14 days, approximately 1 min each day), as described in §4.4. At baseline, mid-point, and post-intervention, participants will be asked to record their body weight with a scale that the study team will provide. Also at baseline and post-intervention, participants will complete questionnaires related to their fatigue, quality of life, symptoms, and a 24-h food recall (approximately 10 min). Post-intervention, we will conduct an exit interview with each participant about their experience with the intervention (10-30 min).

Primary Aim: to assess the adherence of the participants to the 10-h TRE intervention. This will be determined by the percent of days that each participant adheres to the 10-h TRE dietary pattern over the course of the 14-day intervention.

Secondary Aim 1: to assess the retention of participants during the 10-h TRE intervention. This will be determined by the percent of consented participants who provide baseline and post-intervention assessments.

Secondary Aim 2: to assess the safety of the TRE intervention. We will closely monitor instances of adverse events as described by the Common Terminology Criteria for Adverse Events (CTCAE), version 5,² with a special focus on body weight.

Secondary Aim 3: to describe the feasibility of recruiting cancer survivors to a 10-h TRE intervention. The number consented over the number approached will be calculated, and the population (i.e., those approached) will be characterized based on eligibility and willingness to participate.

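### The post-intervention BFI looks back at most 24 hours but may be completed up to 3 days after the 14-day diet, so late forms describe only time after the assigned period

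*Combined protocol and SAP*

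**What the plan says.** Section 4.1 sets the length of the intervention: "All participants in this study will be asked to follow a TRE meal pattern for 14 consecutive days". Section 4.4 describes the BFI: "It captures fatigue *now* and the usual and worst in the last 24 h". The same section gives the FACIT-F a 7-day recall.

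On timing, section 8.2.5 says "it is preferred that post-intervention questionnaires are completed the day after the intervention ends (Day 15), but up to 3 days will be allowed". Section 8.2.4 asks participants to "complete post-intervention assessments within 3 days of completing the intervention". The table in section 8.2.7 places the BFI at about Day 15.

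On its role, section 4.4 says: "An exploratory aim of this study is cancer-related fatigue, as assessed using the FACIT-F, BFI, and Symptom Inventory". Section 17.2 defines the change score as running from baseline to 14 days, tests it with a paired t-test at two-tailed alpha 0.10, and adds: "The magnitude of the change score together with variability and distribution data will be used to inform the sample size".

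**The concern.** An instrument with a 24-hour recall has to be completed within a day of the period that it is meant to describe. The 3-day allowance suits the FACIT-F but not the BFI. The plan does not ask participants to keep the eating window until the forms are done, does not record whether they did, and does not say how a late BFI enters the analysis.

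The schedule handles the other 24-hour measure differently. Section 8.2.5 lets the end-of-intervention Food Record move only earlier, to Day 12 or 13, so that it always describes an intervention day. The BFI may move only later.

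At stake is an exploratory estimate. If some participants drop the pattern after Day 14 and fatigue responds quickly, the BFI change would mix fatigue during and after the assigned period, and would carry that mixture into the planning of the follow-on study.

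**Working it through.** **1. The plan's own figure.** Inputs from section 17.2: n = 32, change of 0.45 SD, two-tailed alpha 0.10, paired t-test. The noncentrality is 0.45 × √32 = 2.546, with 31 degrees of freedom and critical value 1.696. Power from the noncentral t is 80.1%, against 80% stated. The smallest change detectable with 80% power is 0.449 SD, against 0.45 stated. The stated figure is correct.

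**2. Overlap of recall with the intervention.** Assume that Day 14 ends at midnight. For a form completed at hour h of Day k, the hours of a 24-hour recall that fall in the intervention are max(0, 24 − [24(k − 15) + h]).

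| BFI completed | 08:00 | 12:00 | 20:00 | Intervention days in the FACIT-F 7-day recall (approx.) |
|---|---|---|---|---|
| Day 15 | 16 h | 12 h | 4 h | 7 |
| Day 16 | 0 h | 0 h | 0 h | 6 |
| Day 17 | 0 h | 0 h | 0 h | 5 |
| Day 18 | 0 h | 0 h | 0 h | 4 |

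The allowance ends on Day 17 if counted from the end of the intervention (section 8.2.4), or on Day 18 if counted from Day 15. The result is the same either way. Even on Day 15 the item on current fatigue falls after the assigned period. Section 4.4 gives no recall period for the six BFI interference items, so the count applies to the severity items as described there.

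**3. What late forms could do (illustration only).** Let f be the share of late forms and r the share of the change that they still carry. With the SD held fixed, the pooled change is 0.45 × [1 − f(1 − r)]. The documents give neither f nor r, and 0.45 SD is a detectable change, not a predicted one. The last column drops late forms (rounded to 3, 6 and 10 of 32) and tests 0.45 SD in the rest.

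| f | All forms kept, r = 0 | All forms kept, r = 0.5 | Late forms dropped |
|---|---|---|---|
| 10% | 0.405 SD, power 72% | 0.428 SD, power 76% | n = 29, power 76% |
| 20% | 0.360 SD, power 64% | 0.405 SD, power 72% | n = 26, power 72% |
| 30% | 0.315 SD, power 54% | 0.383 SD, power 68% | n = 22, power 65% |

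If half of the change persists, dropping late forms gives no more power than keeping them. It gains power only if the effect fades faster than that. With f = 0 or r = 1 there is no loss at all.

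**The case against.** The case for leaving the plan alone has real force.

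- **Low stakes.** The BFI is exploratory. Section 8.1 does not expect large changes in fatigue and places the hypothesised benefit in a longer intervention. A two-week change without a control group is a weak planning input for a randomised trial in any event. This stands, and it keeps the point small.
- **Other measures cover the intervention.** The diary records average fatigue on each of the 14 days (section 4.3), and a late FACIT-F still covers mostly intervention days. This also stands, although the fatigue analysis in section 17.2 names only the FACIT-F and BFI, with the Symptom Inventory for general symptoms, and not the diary.
- **The allowance is short and open.** Day 15 is the stated preference, and REDCap sends reminders (section 14.3). Late forms may be few, but nothing in the plan says how few.

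A reader might go further and infer that late forms show fatigue off the diet, that power on the BFI falls to one of the lower figures above, or that late forms should leave the main estimate. The documents support none of these. No section says that participants stop at Day 14; they may continue, or effects may carry over. The lower powers need an assumed late share and an assumed rapid loss of effect. Exclusion has its own cost in sample size.

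Moving the BFI to the evening of Day 14 could create a new mismatch, because the baseline BFI has no fixed time of day. That objection is sound, and the fix below allows for it.

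**Conclusion.** The mismatch is real and follows from the plan's own wording. On the recall period given in section 4.4, a BFI from Day 16 or later reflects only time after the assigned 14 days, yet it would count as change from baseline to 14 days. That section 17.2 treats late forms like the rest is inferred from its silence on completion dates.

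The effect on the BFI estimate cannot be quantified from the documents, and it may be nil. The 80% power statement needs no correction. The primary adherence aim and the retention, safety and recruitment aims are untouched. This is a cheap, optional improvement to an exploratory measure.

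**What to change.** - Ask for the post-intervention BFI at the end of Day 14, with the daily diary, and use Day 15 as the fallback. The 24-hour recall then lies wholly inside the intervention.
- Ask for the baseline BFI at a similar time of day, so that the ratings of current fatigue are comparable.
- Record the completion date on electronic and paper forms. Paper versions are allowed (section 8.2.7), so the date field should be on both.
- In section 17.2, keep all BFI forms in the main change estimate, and add a sensitivity analysis that excludes forms dated Day 16 or later.
- Leave the 3-day allowance in place for the FACIT-F.

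The cost is a change of schedule wording, a date field, slightly more burden on Day 14, when the Food Record and diary are also due, and one extra analysis.
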